 - In the case that year of the start date of pre-study period is the same year of the end date of previous flare in the same eye, then use the latest date of both for imputation.
- Completely missing start dates of flares will only be imputed if it is clear based on the end date that the flare occurred within the pre-study period. Then the maximum (latest) of start date of pre-study period and end date of previous flare will be considered.
- Missing end day, but month and year present: Impute the last day of the month unless one of the following conditions apply:
 - Month and year are the same as month and year of the end date of pre-study period, then impute with the end date of pre-study period.
 - Month and year are the same as month and year of the start date of subsequent pre-study flare in the same eye before Baseline, then impute with the start date of subsequent pre-study flare.
 - In the case that month and year of the end date of pre-study period is the same month and year of the start date of subsequent pre-study flare in the same eye, then use the earliest date of both for imputation.
- Missing end day and month, but year present: Impute December 31st unless one of the following conditions apply:

- Year is the same as year of the end date of pre-study period, then impute with the end date of pre-study period.
- Year is the same as year of the start date of subsequent pre-study flare in the same eye, then impute with the start date of subsequent pre-study flare.
- In the case that year of the end date of pre-study period is the same year of the start date of subsequent pre-study flare in the same eye, then use the earliest date of both for imputation.
- Completely missing end dates of flares will only be imputed if it is clear based on the start date that the flare occurred within the pre-study period (of 2 years prior to baseline). Then the minimum (earliest) of end date of pre-study period (i.e. the day prior to treatment start date), the day prior to start date of subsequent pre-study flare in the same eye, or the start date plus the median duration of flare in that subject will be considered. The median duration of flare is determined from all flares recorded for that subject that have complete start and end dates (regardless of eye), including any flares prior to or during the pre-study period and on-study period.

On-study period (Baseline until end of treatment):

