 - Year is the same as year of the end date of on-study period, then impute with the end date of on-study period.
 - Year is the same as year of the start date of subsequent on-study flare in the same eye, then impute with the start date of subsequent on-study flare in the same eye.
 - In the case that year of the end date of on-study period is the same year of the start date of subsequent on-study flare in the same eye, then use the earliest date of both for imputation.
- Completely missing end dates of flares will only be imputed if it is clear based on the start date that the flare occurred after treatment start during the on-study period. Then the start date of subsequent on-study flare in the same eye will be considered. Otherwise it will be assumed to be ongoing.

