8.1.1 Derivations of primary efficacy variable

The primary efficacy variable is the number of distinct episodes of AU flares in the Treatment Period. Per protocol, a flare is considered a new episode if a gap of at least 3 months occurs between 2 flares. If AU flare episodes as reported by the investigator occur less than 3 months

(90 days) apart in the same eye, these will be programmatically corrected, such that a new AU flare within 3 months (90 days) after the end of the previous AU flare in the same eye will be considered as pertaining to the same AU episode. These flares will then be counted as one episode. Otherwise, if the time interval between 2 consecutive AU flares is greater than 3 months (90 days), or a separate eye is affected, the AU flares will be considered as separate episodes.

Pre-study and on-study AU flare episodes will be counted. An episode of AU flares is considered as pre-study, if the start date of flare is before the start date of study medication and if start date of flare occurs within the 24 months (730 days) prior to the start of study medication. For the interim analysis, an episode of AU flares is considered as pre-study if the flare occurs within 48 weeks (336 days) prior to the start of study medication.

For the Week 96 (primary) analysis, an episode of AU flares is considered on-study, if the start date of flare is on or after the start date of study medication and the start date of the flare occurs up to and including the last visit in the treatment period, i.e. Week 96 or discontinuation visit.

Pre-study and on-study flares of the same eye will be combined if the time interval between the end of pre-study flare and the start of subsequent on-study flare is less than 3 months (90 days). The resulting flare episode will be considered as pre-study flare episode.

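### Year-only flare end dates get no duration cap, although completely missing pre-study end dates do; this can inflate total flare duration, with probably little effect on the primary rate ratio

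*SAP*

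**What the plan says.** SAP 4.2 gives separate rules for partly and completely missing flare end dates.

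- **Year-only, pre-study.** The default is 31 December: "Missing end day and month, but year present: Impute December 31st unless one of the following conditions apply". The first exception is the calendar year of Baseline: "Year is the same as year of the end date of pre-study period, then impute with the end date of pre-study period". The second is a later pre-study flare in the same eye: "Year is the same as year of the start date of subsequent pre-study flare in the same eye, then impute with the start date" of that flare. If both apply, the earlier date is used. The length of the flare is not limited.
- **Completely missing, pre-study.** The end is the earliest of the period end, the day before the next same-eye flare, "or the start date plus the median duration of flare in that subject will be considered". The median comes from that subject's flares with complete dates.
- **On-study.** The year-only rule has the same structure as the pre-study one. For a completely missing end date: "Then the start date of subsequent on-study flare in the same eye will be considered"; if there is no such flare, the flare is treated as ongoing.

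The imputed end date is then used twice. SAP 8.1.1 measures the 90-day gap from it, "such that a new AU flare within 3 months (90 days) after the end of the previous AU flare in the same eye" belonging to the same episode. The same gap applies across Baseline ("Pre-study and on-study flares of the same eye will be combined if the time interval" is under 90 days), and the combined episode is counted as pre-study. SAP 8.3.1 computes duration as end minus start plus 1 and summarises each subject's total duration before and during the study.

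SAP 8.1.2 repeats the primary analysis without subjects who have completely missing pre-study end dates. Subjects with year-only dates stay in. It also analyses flares as the investigator reported them, without the 3-month correction.

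**The concern.** A record that carries the year is normally better than one that carries nothing. Here it is often treated worse: the year-only flare can run for many months, while the undated one stops at a typical length for that subject. SAP Amendment 3 introduced both the median cap and the exclusion analysis for completely missing pre-study end dates. The year-only branch received neither.

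Three consequences follow from sections 4.2, 8.1.1 and 8.3.1 read together:

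- distinct same-eye flares can be fused, in either period;
- a same-eye flare early on CZP can be recounted as pre-study, because the pre-study flare now appears to end at or near Baseline;
- flare duration, a listed efficacy variable and part of a study objective, is lengthened.

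The study compares retrospective with prospective records in the same subjects. If incomplete dates are commoner in the retrospective part, the distortion differs between the two periods.

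**Working it through.** **Planning inputs.** SAP 2.4 gives 0.292 flares per year before the study, 0.146 on CZP, 1.5 years, two-sided alpha 0.049, 80% power and N=86. Signorini's two-group formula, halved per group:

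N = ½ × (2z_α + z_β√(2 + 2r0/r1))² / (r0 × T × ln(r1/r0)²) = ½ × (3.937 + 2.061)² / (0.292 × 1.5 × 0.4805) = 85.5, rounded up to 86.

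The plan's figure is reproduced, so these rates are used below. The plan gives no figure for the date rules themselves.

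**Dates by hand.** The pre-study period is taken to end the day before treatment, as 4.2 explains it in the rule for completely missing dates.

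- Start 1 Feb 2017, end 2017, Baseline 1 Sep 2017. Imputed end 31 Aug 2017; duration 28+31+30+31+30+31+31 = 212 days. A same-eye on-study flare up to 28 Nov has a gap of at most 89 days and becomes part of a pre-study episode. With the end date wholly missing and an assumed 42-day median, the end would be 15 Mar 2017, the gap to 28 Nov would be 258 days, and there would be two episodes.
- Start 1 Feb 2016, end 2016, next same-eye flare 1 Nov 2016. Imputed end 1 Nov 2016; the first flare lasts 275 days and the gap is 0, so the two always merge. The merged episode also includes the second flare.
- End 2017, next same-eye flare 15 Mar 2018, Baseline June 2018. Imputed end 31 Dec 2017; gap 31+28+15 = 74 days; merged.
- End 2017, Baseline 20 Jan 2018, same-eye on-study flare 10 Mar 2018. Imputed end 31 Dec 2017; gap 31+28+10 = 69 days; recounted as pre-study.

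**Simulation.** Truly distinct flares (same-eye gap at least 90 days), Baseline uniform over a calendar year, 730 days before and 672 days on study, generating rate ratio 0.5. Assumptions not in the documents: median flare 42 days, 70% of flares in one eye, and the share of year-only end dates, placed pre-study only unless stated.

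| Pre-study rate per year | Year-only share | Pre-study count | On-study count | Rate ratio, true to imputed | Total pre-study duration |
|---|---|---|---|---|---|
| 0.292 | 10% | -0.5% | -0.1% | 0.513 to 0.516 | x1.31 |
| 0.292 | 30% | -1.6% | -0.3% | 0.514 to 0.521 | x1.98 |
| 1.0 | 10% | -1.6% | -0.4% | 0.528 to 0.534 | x1.31 |
| 1.0 | 30% | -5.0% | -0.9% | 0.530 to 0.553 | x1.91 |
| 1.5 | 10% | -2.2% | -0.4% | 0.540 to 0.550 | x1.30 |
| 1.5 | 30% | -6.6% | -1.2% | 0.553 to 0.585 | x1.90 |

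The true ratios exceed 0.5 because starts within 90 days of a same-eye flare were dropped.

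- Median flare 28 or 60 days (0.292 per year, 30%): duration x2.44 or x1.64.
- 30% year-only in both periods (0.292 per year): x1.95 pre-study and x1.92 on-study.
- Median cap applied to year-only dates (30%, using the 42-day population median and without the 1 January floor proposed below): rate ratio 0.514 against 0.514 true at 0.292 per year and 0.531 against 0.530 at 1.0 per year; duration 0.98 to 0.99 of true.

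**In flares, at the planning rates with 30%.** Pre-study: 86 × 2.00 × 0.292 = 50.2 expected, and 1.6% of that is 0.8. On-study: 86 × 1.84 × 0.146 = 23.1 expected, and 0.3% of that is 0.07.

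**The case against.** A reader might infer that these rules tilt the primary result toward CZP. The documents do not support that. Recounting an early on-drug flare as pre-study does lower the on-study count, but it adds no historical episode and is rare. Fusing historical flares lowers the pre-study count and works against CZP. It was the larger effect in every simulated scenario, and the rate ratio always moved toward 1. The 8.1.2 analysis of investigator-reported flares also protects the counts: flares are assigned to periods by start date, and without merging the gap from the end date plays no part.

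Nor is historical duration inflated in CZP's favour by construction. The on-study year-only rule is the same, and with equal shares the two periods were inflated almost equally. An advantage for CZP needs year-only dates to be commoner in the retrospective records, which is plausible but not documented. Duration is a descriptive variable among analyses that SAP 8 calls exploratory.

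Two further readings go too far. A year-only record is not always treated worse than an undated one: if the subject has no flare with complete dates, the median is undefined and the undated flare can run to the day before treatment. And an undated on-study flare is not always merged into the next one, because without a later same-eye flare it is treated as ongoing.

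These objections settle direction and importance for the primary endpoint. They do not answer the inconsistency between the two rules, and no planned analysis shows how far duration depends on year-only dates.

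**Conclusion.** The point holds as a weakness in the imputation rule that mainly affects total flare duration. If the assumed shares and the 42-day median apply, historical duration is about 1.3 times its true value with 10% year-only dates and 1.9 to 2.0 times with 30%. A shorter typical flare makes it worse and a longer one better. The comparison with on-study duration favours CZP only if year-only dates are commoner pre-study.

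For the primary rate ratio the net effect is probably small and toward 1: a shift of 0.003 to 0.010 with 10% year-only dates and, at the planning rate, 0.007 with 30%. The documents give neither the share of year-only dates, nor flare length, nor the split between eyes, so the sizes are illustrations. The change should be made because it is cheap and uses tools already in the SAP; the primary conclusion does not hang on it.

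**What to change.** In SAP 4.2, for year-only end dates in both periods, use the earliest of:

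- the date now stated;
- the day before the next same-eye flare;
- start plus the subject's median duration over flares with complete dates;

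but never earlier than the flare's start or 1 January of the recorded year. The floor is needed: start 1 Dec 2016, end 2017 and a 21-day median would otherwise give 22 Dec 2016, outside the recorded year. Leave end dates with month and year as they are, since a cap could contradict the recorded month.

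State a fallback for subjects with no complete flare, for example the median across all subjects. In 8.1.2, extend the analysis that excludes subjects with completely missing pre-study end dates to those with year-only ones. Next to the duration summary in 8.3.1, report the number of imputed end dates by period, so that the reader can judge whether the two periods are comparable.

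The cost is minor SAP wording and programming, and a somewhat smaller set in the sensitivity analysis.

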- Missing end day and month, but year present: If the maximum of the subject's date of study termination or the date equivalent to 70 days after the subject's last intake of study medication is the same year as the occurrence of the AE/Concomitant medication, then the end day and month will be set to the maximum of the date of study termination or the date equivalent to 70 days after last intake of study medication. Otherwise the end day will be set to December 31st of the given year.

Efficacy variables

The start and end dates of flares will be imputed for the analyses of AU flares data, in order to allow the calculation of time intervals between 2 consecutive flares and the duration of flares. Different rules will be applied for pre-study and on-study period flares.

For the interim analysis, the pre-study period is starting 48 weeks prior to Baseline, i.e. 336 days prior to Baseline until Baseline. The on-study period for the interim analysis is starting from Baseline until week 48, i.e. until study day 336.

For the final analysis, the pre-study period is starting 24 months prior to Baseline, i.e. 730 days prior to Baseline until Baseline. The on-study period for the final analysis is starting from Baseline until week 96, i.e. until the date of the Week 96 or discontinuation visit. In addition, sensitivity and supportive analyses use different definitions (as defined in Section 8.1.2).

Pre-study period:

- Missing start day, but month and year present: Impute the first day of the month unless one of the following conditions apply:
 - Month and year are the same as month and year of the start date of pre-study period, then impute with the start date of pre-study period.
 - Month and year are the same as month and year of the end date of previous flare in the same eye, and the end date is clearly greater than end date of previous flare, then impute with the end date of previous flare.
 - In the case that month and year of the start date of pre-study period is the same month and year of the end date of previous flare in the same eye, then use the latest date of both for imputation.
- Missing start day and month, but year present: Impute January 1st unless one of the following conditions apply:
 - Year is the same as year of the start date of pre-study period, then impute with the start date of pre-study period.
 - Year is the same as year of the end date of previous flare in the same eye, then impute with the end date of previous flare.

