8 EFFICACY ANALYSES

The efficacy analysis will be based on all subjects in the SS or FAS, as appropriate. If there is no missing AU flare incidence data from pre-study period, the FAS will be the same as the SS. The FAS will be used for analyses of the primary variable and the SS will be used for all other efficacy analyses. The primary efficacy analysis will additionally be repeated for the PPS.

All statistical analyses besides the primary efficacy analysis will be exploratory in nature only. Any p-values or confidence intervals produced in association with secondary or other analyses will be considered non-confirmatory.

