8.1.2 Supportive and sensitivity analyses of the primary efficacy variable

The primary efficacy analysis will be repeated in the subgroup of subjects with at least 1 documented AU flare within 12 months prior to Baseline.

The AU flares as reported by the investigators, without programmatically correcting for the 3 month interval between 2 flares, will be analyzed in addition to the primary efficacy variable of protocol-defined AU flares at least 3 months apart.

The primary analysis will be repeated using the pre-study period as 96 weeks (672 days) prior to start of study medication for counting flares and as the offset, instead of 24 months. The on-study period will be the same as that used for the primary analysis.

In addition, the analysis for the full 2 years before and after study medication will be provided. The pre-study period will be the 2 years (730 days) prior to start of study medication, which will be used for counting flares and as the offset. The on-study period will be determined for whose episodes of AU flares for which the start date of flare is on or after the start date of study

medication and up to and including the SFU visit or date of last administration of study medication + 70 days.

An analysis for the first 48 weeks will also be produced. The period for pre-study will be the 12 months (365 days) prior to start of study medication, which will be used for counting flares and as the offset. An episode of AU flares will be considered on-study, if the start date of flare is on or after the start date of study medication and up to and including the Week 48 visit or discontinuation visit if prior to Week 48. The exact date of the Week 48 or discontinuation visit will be used for each subject. This analysis will also be repeated using 48 weeks (336 days) as the pre-study period for counting flares and as offset, but keeping the on-study period of 48 weeks the same (i.e. using the exact date of the Week 48 or discontinuation visit).

The primary efficacy analysis will be repeated in the subgroup of subjects excluding those with any pre-study flares with completely missing end dates in the 2 years prior to baseline. Subjects will be excluded if any of the flares that started within the 2 years prior to baseline have completely missing end dates (i.e. no day, month or year)

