8.3.1 Flare assessments

For each subject in FAS, the total duration and the maximum severity of pre-study and on-study AU flares will be determined and summarized. The duration of an episode of AU flare (T_{Dur_Fl}) is calculated as follows:

$$T_{Dur_Fl} = Date_{End_Fl} - Date_{Start_Fl} + 1$$

with $Date_{End_Fl}$ and $Date_{Start_Fl}$ the end date and start date of flare, respectively. The duration of pre-study and on-study periods is defined in Section 4.2.

For the interim analysis, the pre-study period is starting 48 weeks prior to Baseline, i.e. 336 days prior to Baseline until Baseline. The on-study period for the interim analysis is starting from Baseline until week 48, i.e. until study day 336.

For the final analysis, the pre-study period is starting 24 months prior to Baseline, i.e. 730 days prior to Baseline until Baseline. The on-study period for the final analysis is starting from Baseline until week 96, i.e. until the date of the Week 96 or discontinuation visit.

The highest grade (severity) of uveitis flare across all flares per subject will be summarized. The highest grade (severity) noted during an episode of uveitis will be graded as follows: Grade 0=None; Grade 1+=Faint; Grade 2+=Moderate, iris and lens details clear; Grade 3+=Marked, iris and lens details hazy; Grade 4+=Intense, fibrin or plastic aqueous; ND=Not done or not assessed; UNK=Unknown

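### The rule for a pre-study flare with no end date pools on-CZP flare durations and has no fallback when the subject has no fully dated flare, so the exploratory historical duration summary can be biased either way

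*SAP*

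**What the plan says.** SAP 4.2 has a separate rule for pre-study flares whose end date lacks day, month and year. It takes the earliest of three candidates. One is the day before first dose: "Then the minimum (earliest) of end date of pre-study period (i.e. the day prior to treatment start date". The other two are "the day prior to start date of subsequent pre-study flare in the same eye, or the start date plus the median duration of flare". The median is computed subject by subject, from flares "that have complete start and end dates (regardless of eye), including any flares prior to or during the pre-study period and on-study period". Partly missing end dates follow other rules and use no median.

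The final-analysis window is 730 days: "the pre-study period is starting 24 months prior to Baseline, i.e. 730 days prior to Baseline until Baseline".

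On-study flares with no end date are handled differently. They end at the next same-eye on-study flare if there is one. "Otherwise it will be assumed to be ongoing".

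The imputed dates have two uses:
- **Duration.** SAP 8.3.1 says that for each subject "the total duration and the maximum severity of pre-study and on-study AU flares will be determined and summarized".
- **Episode counting.** SAP 8.1.1 joins same-eye flares less than 90 days apart into one episode.

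SAP 8 gives the status of the duration summary: "All statistical analyses besides the primary efficacy analysis will be exploratory in nature only". SAP 8.1.2 repeats the primary count analysis in the "subgroup of subjects excluding those with any pre-study flares with completely missing end dates in the 2 years prior to baseline". Nothing equivalent is planned for duration.

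**The concern.** There are two separate problems.

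**Donors from the treated period.** Flare duration is summarised for the period before CZP and the period on CZP. The rule fills gaps in the first with values that may come from the second. If CZP shortens flares, the historical figure is drawn toward the treated one.

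**No rule without a donor.** If the subject has no flare with complete start and end dates, the median does not exist and the SAP is silent. Dropping the undefined candidate leaves the day before the next same-eye pre-study flare or the day before first dose. A flare that started long before Baseline would then be recorded as lasting months or years.

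At stake is the descriptive pre-study duration summary and, in one narrow configuration, the historical episode count.

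**Working it through.** **Plan figure, to check the rates used below.** The documents give no figure for imputed duration. The rates come from SAP 2.4: 29.2 flares per 100 subject-years before CZP, 14.6 on CZP (ratio 0.5), mean follow-up 1.5 years, two-sided alpha 0.049, power 80%. The Poisson-regression formula that the plan cites, for two equal groups, gives

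N total = (z_α/2·√4 + z_β·√(2 + 2/0.5))² / (1.5 × 0.292 × (ln 0.5)²) = (1.969 × 2 + 0.842 × 2.449)² / 0.2104 = 171.0,

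or 85.5 per group, rounded up to the plan's 86.

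**Assumptions not in the documents.** True pre-study flares of 42 days and on-CZP flares of 21 days (ranges below), 5–40% of pre-study flares with no end date at all, and either eye equally likely.

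**Effect of on-CZP donors.**
- One dated 42-day pre-study flare and one dated 21-day on-CZP flare: median (42 + 21)/2 = 31.5 days.
- Only the on-CZP flare dated: 21 days.
- Pre-study donors only: 42 days.

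**No donor, read literally.** Duration under SAP 8.3.1 is end − start + 1, with the end at Day −1:

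| Start | No later same-eye flare | Next same-eye flare 120 days later |
|---|---|---|
| Day −730 | 730 days | 120 days |
| Day −365 | 365 days | 120 days |
| Day −90 | 90 days | not possible |
| Day −30 | 30 days | not possible |

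**How often, and how much.** Expected pre-study flares in 86 subjects: 86 × 0.292 × 2 ≈ 50. With Poisson counts and no flares recorded before the window, P(no other pre-study flare) = exp(−0.584) = 0.56 and P(no on-study flare) = exp(−0.146 × 1.84) = 0.76. Their product is P(no donor) = 0.43. A no-donor flare with a uniform start is given about 365 days on average. With 10% of end dates missing, the overstatement of historical flare-days is about 0.10 × 0.43 × (365 − 42)/42 = 0.33.

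Coding the rule as written for 86 subjects gives this ratio of imputed to true historical flare-days:

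| Assumed pre-study/on-CZP days | 5% missing | 10% | 20% | 40% |
|---|---|---|---|---|
| 42/21 | 1.18 | 1.33 | 1.73 | 2.53 |
| 28/14 | 1.27 | 1.52 | 2.09 | 3.56 |
| 90/45 | 1.07 | 1.13 | 1.29 | 1.65 |

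These are upper-end values, because no dated flares from before the 730-day window were simulated and the SAP allows them as donors. The same-eye cap applied in about 0–6% of no-donor cases.

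A second simulation lets flare rates vary between subjects (gamma, variance 1) and allows an average of 0 to 2 recorded flares per subject before the window (42-day flares, 28-day on-CZP donors). It gives 1.06–1.23 at 10% missing and 1.14–1.49 at 20%. The no-donor share of undated flares is 30–33% without flares from before the window and 8–16% with one or two. In a further 1–13% the only donor is an on-study flare. In the trial, 5–10 undated flares × 8–33% is about 0.4–3.3 no-donor flares.

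**Effect on the count.** Take a subject with two same-eye pre-study flares, the first with no end date, and no fully dated flare. The first is imputed to end the day before the second starts. The 90-day rule then counts one episode even if they began, say, 400 days apart. This lowers the historical count, which works against CZP.

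**The case against.** Much of the opposing case stands.

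- **Status.** Duration is an "other" variable, summarised descriptively with no test or planned contrast. The median is also reported, and it is less sensitive than the mean to a few long imputed values.
- **Rarity.** The rule applies only when day, month and year are all missing. The protocol's Screening visit reviews all documented uveitis history, so dated flares from before the window may be available as donors. The documents give neither the missing share nor flare durations.
- **Direction.** Borrowing on-CZP durations matters only if CZP shortens flares, which the documents do not show. If it does, historical time is understated, which works against CZP. The no-donor case usually works the other way. The two need not cancel.

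Three stronger readings are tempting and are not supported:

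- **A reader might infer that historical time is grossly overstated.** That needs an undated end, no donor, no later same-eye flare and a start well before first dose. It also rests on one literal reading of a silent rule.
- **A reader might infer that only the historical side can be inflated.** The SAP does not say how an on-study flare assumed to be ongoing enters the duration formula, which needs an end date. If it is cut at the end of the period, it could also run long.
- **A reader might infer that a flare run to Day −1 absorbs same-eye flares in the first 90 days on CZP and so removes them from the primary count.** A fully dated on-study flare is itself a donor, so the run to Day −1 does not arise. The simulation, with on-study flares fully dated, lost none. The effect needs the on-study flare to be incompletely dated as well.

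What remains is a donor pool that expressly mixes the two periods, and a stated minimum with an undefined term.

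**Conclusion.** The point holds for the pre-study duration summary. The pooling of on-CZP durations is explicit; the missing fallback is a gap that the literal rule fills with durations of up to about 730 days. The bias can go either way and the documents do not fix its size. Per flare, it is 31.5 or 21 days instead of an assumed 42 through pooling, and up to about 730 days without a donor. For total historical flare-days at 10% missing, the illustrations run from 1.06 to 1.52 times the true value, depending on assumed durations, between-subject variation and recorded history. They may concern only a handful of flares.

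The primary count is largely protected, both because dated on-study flares are donors and because SAP 8.1.2 repeats the analysis without the affected subjects. The remaining effect, joining distant same-eye pre-study flares in a subject with no fully dated flare, lowers the historical count and is covered by that repeat when the subject has a completely undated flare end. This warrants a change to an exploratory summary. It does not threaten the primary conclusion.

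**What to change.** In SAP 4.2, for completely missing pre-study end dates:

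1. Take the median from fully dated pre-study flares only: the subject's own if there are any, otherwise the median over all fully dated pre-study flares in the trial. Use no on-study flares.
2. Keep the caps at the day before the next same-eye pre-study flare and the day before first dose.
3. In SAP 8.3.1, add a duration summary that excludes flares with imputed end dates.

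The cost is SAP wording and a little more programming, with no new data. The trade-off is that a trial-wide median ignores differences in flare duration between subjects; the added summary shows whether that matters.
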